4.4. Minimization of Bias

Potential sources of bias in this study may result from the Hawthorne effect, selection of study centers, selection of subjects, treatment of subjects, and evaluation of study data. The following methods have been incorporated into the study to minimize potential bias.

- Center selection criteria, documented under separate cover, will need to be met prior to participation in Brady MX. Study center characteristics will be collected at activation on possible differences that may affect the primary endpoints. Centers will be used as their own control
- Subjects will be screened to confirm eligibility with the help of screening logs, for enrollment with defined inclusion/exclusion criteria prior to enrollment
- Subject demographics will be collected at baseline on possible differences that may affect the primary endpoints
- It is anticipated that the distribution of subjects with various co-morbidities will vary by study centers. To minimize potential bias, all sites will be encouraged to enroll at least 5 subjects in each study Phase and enrollment at a site cannot exceed 42 subjects per phase to ensure a more even distribution of data
- All study Clinicians will be required to follow the Clinical Investigation Plan
- All study clinicians and Medtronic personnel will be trained on their respective aspects of the clinical investigation plan using standardized training materials.

5. STUDY PROCEDURES

All local requirements will be fulfilled prior to center activation and enrollment of subjects into the study. Each study site must have written documentation of site and investigator readiness, including (but not limited to):

Medical Ethics Committee (MEC), or Head of the Medical Institution written approval of the current version of the Clinical Investigation Plan and Patient Informed consent/Patient Data Release (what is applicable depending on the site)

When MEC or Head of the Medical Institution written approval is submitted to Medtronic the following needs to be included:

- The approval letter must contain enough information to identify the version/date of the documents approved or it must be retrievable from the submission letter.
- Approval letter must be accompanied by a roster or written documentation that center staff participating in the study did not participate in the approval process

Investigator Curriculum Vitae on file with the sponsor (signed and dated as required per geography/country)

- Signed/dated Clinical Trial Agreement on file with the sponsor

Signed/dated documentation of training of required personnel

All clinical investigators managing the subjects must be qualified practitioners that will be involved in the diagnosis and/or treatment of subjects with SND. All implanting physicians must be experienced in the handling of market released pacemakers. All participating Clinicians will complete study training regarding the Informed Consent Process (if applicable), case report forms and Clinical Investigation Plan.

Medtronic will inform the investigator in writing when all requirements have been fulfilled for center activation.

The following study equipment may be useful to have available at each center to support study activities.

:

- Electrocardiography machine
- Echocardiography machine
- Holter monitor, Event Monitor or Insertable Cardiac Monitor
- Ergometer or treadmill.

5.1. Informed Consent/Patient Data Release Process

Patient Informed Consent(PIC)/Patient Data Release (PDR) is defined as legally effective, documented confirmation of a subject's (or their legally authorized representative or guardian) voluntary agreement to participate in a particular clinical investigation after information has been given to the subject on all aspects of the clinical investigation that are relevant to the subject's decision to participate. A PDR can only be used when ethics committee approval of the study is not needed or when local laws allow.

Prior to enrolling patients, each investigational center's Medical Ethics Committee (MEC), or Head of the Medical Institution must approve the Clinical Investigation Plan (CIP) and Patient Informed Consent/Patient Data Release (PIC/PDR). Any changes to the PIC/PDR consent must be approved by Medtronic and the MEC or Head of the Medical Institution reviewing the application before being used to consent a prospective study subject. The document(s) should be controlled (i.e. versioned and/or dated) to ensure it is clear which version(s) were approved by the MEC/IRB or Head of the Medical Institution.

Prior to initiation of any study-specific procedures, subjects (or their legally authorized representative or guardian) must sign and date the data protection authorization and/or other privacy language where required by law and the MEC or Head of Medical Institution and Medtronic approved Patient Informed Consent/Patient Data Release. A copy of the PIC/PDR form or a signed copy where required by law, will be given to all subjects (or their legally authorized representative or guardian) in a language he/she is able to read and understand.

The process of obtaining patient informed consent shall:

- Avoid coercion and undue influence of subjects to participate
- Answer all questions to the subject's satisfaction
- Not waive or appear to waive subject's legal rights
- Use language that is non-technical and understandable to the subject
- Provide ample time for the subject to consider participation
- Include a dated signature of the subject acknowledging that their participation in the study is voluntary
- Include a dated signature by the clinical investigator or authorized designee

If the PIC/PDR is obtained the same day the subject begins participating in study related procedures, it should be documented in the subject's case history that consent was obtained prior to participation in any study-related procedures. In the event the subject cannot read and/or write, witnessed (impartial third party) informed consent will be allowed, provided detailed documentation of the process is recorded in the subject's case history, the witness was present during the entire discussion and the witness signs and dates the PIC/PDR to attest that the information was accurately explained, and clearly understood by the patient and that consent was freely given. The original or a copy of the signed PIC/PDR must be filed in the hospital/clinical chart or with the subject's study documents. A copy of the signed

PIC/PDR and data protection authorization/or other privacy language where required by law must be provided to the subject.

The PIC/PDR consent form and data protection authorization and/or other privacy language where required by law must be available for monitoring and auditing. Any Medtronic Field personnel who supports the study must be able to review the subject's signed and dated consent form and verify it's completeness prior to proceeding with study related activities. In the event the Medtronic Field personnel identify a consent as being incomplete, the study activities will not be allowed to occur until the consent of the subject can be adequately and appropriately obtained.

5.2. Data Collection

Table 1 depicts the data collection requirements for the study.

Table 1: Data Collection and Study Procedure Requirements at Subject Visits

Study procedure	Enrollment Baseline	Diagnostic Assessment	Implant
Informed Consent/ Medical release	X		
Inclusion / Exclusion	X		
Demographics	X		
Medical History	X		
Symptoms	X		
Vitals (HR, BP)	X		
Cardiovascular Medications	X	X	X
Diagnostic tests/ results	X if applicable	X	
Final Diagnosis		X	
Device Indication		X	
System information			X
Pt Education tool used (Phase II only)		X	
Treatment decision		X	
Death	As they occur		
Reason for exit			

5.3. Enrollment/Baseline Procedures

The investigator or designated study coordinator will evaluate patients for inclusion and exclusion criteria. Patients who meet these criteria may be invited to participate in the study. Each study subject or legal representative must sign an informed consent/Patient Data Release prior to any study procedures taking place.

Enrollment is anticipated to occur prior to a final diagnosis of the patient being known, however, the patient may be enrolled at any time after the Brady MX inclusion/exclusion criteria are met.

When a subject signs and dates the patient consent form/Patient Data Release, he/she is considered a subject enrolled in the study. The date the subject signed the consent form must be reported in the CRF. The Baseline assessment will be utilized to collect subject demographic data, cardiovascular medical history, symptoms, vital signs and cardiovascular medication use.

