11.1. Primary Objective(s)

Primary Objective #1

Evaluate the impact of the intervention on the diagnosis of SND.

Hypothesis

The primary objective will be tested with the following hypothesis:

$$H_0: p_{1t} = p_{2t}$$

$$H_A: p_{1t} \neq p_{2t}$$

where p_{1t} is the proportion of patients with SND in Phase I and p_{2t} is the proportion of patients with SND in Phase II at time point t .

Endpoint Definition

The absolute change in the proportion of subjects diagnosed with SND at pre-specified time points ($\% = \text{number diagnosed} / \text{number enrolled} \times 100$ at time point $t = 6$, or t is a multiple of 6 representing any additional 6-month interval for which there is sufficient follow-up information) and the absolute change in the number of subjects diagnosed with SND per person-year.

Analysis Methods

A. Statistical Methodology

To compare the proportion of subjects with an SND diagnosis pre-intervention (Phase I) to the proportion post-intervention (Phase II), a binomial exact test will determine statistical significance. The proportion of subjects diagnosed will be evaluated at multiple time points because the time to diagnosis is expected to vary by hospital. Thus, times are pre-specified starting at 6 months and any additional 6-month interval thereafter for which there is sufficient follow-up data available to compare study phases. Proportions calculated at all available time points will be reported. Additionally a Poisson regression will compare the average number of subjects with an SND diagnosis in Phase I and Phase II where the subject time in study is treated as an offset in the model. The above described tests will be performed separately within site as well as overall.

B. Determination of Patients/Data for Analysis

All subjects that are enrolled in the study and that meet study inclusion/exclusion criteria will be included in the determination of the proportion estimates. The proportion estimates will be calculated based on information from fixed time points at 6 months of follow-up, and any additional 6-month interval thereafter for which there is sufficient follow-up data available to compare study phases. The number of subjects that obtain a SND diagnosis by pre-specified time point t is included in the numerator and the number of subjects enrolled is included in the denominator.

Sample Size Methods and Assumptions

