The proportion of SND diagnoses in subjects with bradycardia is currently unknown. The power calculations conservatively assume that the SND diagnosis will be 10% at six months of follow-up, or equivalently an SND incidence of 0.2 diagnoses per person-year. If 200 subjects are collected each in Phase I and in Phase II, assuming a type I error of 0.05 and power of 0.80, a binomial exact test will detect an increase in SND diagnosis of at least 10%. For example, the study will find a statistically significant difference between a Phase I SND percentage of 10% at 6 months and a Phase II SND percentage of 20% at 6 months. If the proportion of SND diagnoses is smaller than 10%, there will be more power to detect significant differences in the diagnosis proportion. It is expected that the study attrition rate may be 5% of the study population. To account for attrition, the sample size for Phase I will be a minimum of 210 subjects and for Phase II will be a minimum of 210 subjects.

Primary Objective #2

Evaluate the impact of the intervention on SND subjects receiving a referral for an indicated IPG device.

Hypothesis

The primary objective will be tested with the following hypothesis:

$$H_0: p_{1t} = p_{2t}$$

$$H_A: p_{1t} \neq p_{2t}$$

where p_{1t} is the proportion of patients referred for an IPG in Phase I and p_{2t} is the proportion of patients in Phase II at time point t .

Endpoint Definition

The absolute change in the proportion of subjects receiving therapy referral for an indicated IPG at pre-specified time points ($\% = \text{number receiving IPG}/\text{number with SND diagnosis} \times 100$ at time point t where $t = 3, 6$, and any additional 3-month interval for which there is sufficient follow-up information) and the absolute change in the number of subjects implanted per person-year.

Analysis Methods

Statistical Methodology

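### Enrollment may follow the final diagnosis, and Objective #1 does not require the SND diagnosis to come after consent, so patients already diagnosed at consent can count as successes

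*Combined protocol and SAP*

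**What the plan says.** Section 5.3 first states an expectation: "Enrollment is anticipated to occur prior to a final diagnosis of the patient being known". The same sentence then gives a wider permission: "the patient may be enrolled at any time after the Brady MX inclusion/exclusion criteria are met". Enrollment is the signing of consent, and it is by invitation: "Patients who meet these criteria may be invited to participate in the study".

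For Objective #1, section 11.1 part B defines the analysis set: "All subjects that are enrolled in the study and that meet study inclusion/exclusion criteria will be included". The numerator is "The number of subjects that obtain a SND diagnosis by pre-specified time point" t, and the denominator is the number enrolled. This sets an upper time limit and no lower one.

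Several places point towards new diagnoses:
- the verb in that numerator, and time points counted in months of follow-up;
- the sample size text, which restates 10% at six months as "or equivalently an SND incidence of 0.2 diagnoses per person-year";
- section 5.2 ("Table 1: Data Collection and Study Procedure Requirements at Subject Visits") and section 5.4, which have the final diagnosis recorded at a visit after enrollment.

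None of the legible criteria in section 4.2 excludes known SND, but part of the exclusion list is not shown. Appendix B says that the case report forms (CRFs) were still being developed.

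**The concern.** A patient who already carries an SND diagnosis when signing consent is a certain success for Objective #1. Recording the diagnosis at a later visit fixes when it is written down, not when it was made. The plan followed as written can therefore mix existing diagnoses with new ones in a primary endpoint.

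Two consequences follow. If the share of such patients differs between phases, the comparison is biased in the direction of the difference. If the share is equal, the bias under the null disappears but a real effect is diluted. A difference is possible because the phases are sequential and unblinded, the workshop comes before Phase II enrollment, and investigators choose whom to invite. Ancillary Objective #4 itself asks whether the intervention changes screening and enrollment.

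**Working it through.** **Inputs.** From section 11.1: "If 200 subjects are collected each in Phase I and in Phase II", 10% against 20% at six months, two-sided hypotheses, type I error 0.05, power 0.80 and a binomial exact test, taken here as the two-sided Fisher exact test. The shares already diagnosed at consent, s1 (Phase I) and s2 (Phase II), are assumptions; the documents give none.

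**The plan's own figures.** The two-sided normal approximation needs 199 per phase, and 200 gives power 80.2%, so the stated sample size is reproduced. Fisher's exact test by full enumeration gives 76.8% at 200 per phase, which is the reference below. The incidence is also consistent: 0.10 / 0.5 year = 0.2 per person-year.

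**Formula.** With true new-diagnosis rate p, the observed rate is s + (1 − s) × p. For example, s = 5% and p = 10% give 0.05 + 0.95 × 0.10 = 14.5%.

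**No intervention effect (p = 10% in both phases, 200 per phase):**

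| s1 vs s2 | Observed rates | Rejection |
|---|---|---|
| 0 vs 0% | 10.0 vs 10.0% | 3.4% |
| 5 vs 5% | 14.5 vs 14.5% | 3.6% |
| 4 vs 5% | 13.6 vs 14.5% | 4.2% |
| 3 vs 5% | 12.7 vs 14.5% | 6.1% |
| 0 vs 2% | 10.0 vs 11.8% | 6.5% |
| 2 vs 5% | 11.8 vs 14.5% | 9.7% |
| 0 vs 3% | 10.0 vs 12.7% | 10.4% |
| 5 vs 10% | 14.5 vs 19.0% | 18.7% |
| 0 vs 5% | 10.0 vs 14.5% | 23.1% |

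What matters is the difference between shares, not their level. The last two rows are extreme: they need 10/19 = 53% and 5/14.5 = 34% of Phase II diagnoses to precede consent.

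**True effect, with 10% and 20% read as new-diagnosis rates.** Equal shares shrink the difference to (1 − s) × 10 points:

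| Share in both phases | Observed rates | Power |
|---|---|---|
| 0% | 10.0 vs 20.0% | 76.8% |
| 1% | 10.9 vs 20.8% | 73.9% |
| 2% | 11.8 vs 21.6% | 71.0% |
| 5% | 14.5 vs 24.0% | 63.0% |

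A larger share in Phase I costs more: 5 vs 3% gives 14.5 vs 22.4% and power 48.0%.

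**After restricting Objective #1 to subjects undiagnosed at consent, without replacement:**

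| Removed, Phase I vs II | n | Null rejection | Power |
|---|---|---|---|
| 3 vs 5% | 194 / 190 | 4.1% | 76.8% |
| 5 vs 5% | 190 / 190 | 3.3% | 74.7% |
| 10 vs 10% | 180 / 180 | 3.2% | 71.7% |

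**If the removed diagnoses are intervention effects.** Suppose that a fraction r of Phase II diagnoses is removed and none in Phase I. The Phase II rate becomes 0.20 × (1 − r) / (1 − 0.20 × r):
- r = 10%: 0.18 / 0.98 = 18.4%, n = 200 / 196, power 64%.
- r = 15%: 0.17 / 0.97 = 17.5%, n = 200 / 194, power 54%.
- r = 25%, as could happen if same-day diagnoses were dropped: 0.15 / 0.95 = 15.8%, n = 200 / 190, power 38%.

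**The case against.** The strongest reply is that the endpoint already reads as new diagnoses. The numerator wording, the follow-up time points, the incidence figure and the person-time offset all assume subjects still at risk at consent, and section 5.3 expects consent to come first. This shows intent and stands as such. It excludes nobody, because the permission in section 5.3 is explicit and section 11.1 part B includes every eligible enrolled subject.

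An exclusion for known SND could sit in the part of the list that is not shown. That cannot be ruled out, and the point depends on it.

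The plan has some safeguards: the consent date, baseline medical history, earlier test results where applicable, screening logs, common criteria, and each center as its own control. They could reveal the problem and make a partial imbalance more plausible than an all-or-none one. None is tied to the analysis set.

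The power losses from equal shares also depend on a reading. If 10% and 20% are totals of diagnosed over enrolled, they already include such patients, and power at 200 stays at 77%.

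Finally, restricting the set has its own risk. A Phase II diagnosis made after the workshop but before consent may be an effect of the intervention, and the restriction removes it. This stands, and it is why the all-enrolled result should be kept as a sensitivity analysis.

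**Conclusion.** The gap is real: as written, the plan can count patients already diagnosed at consent as Objective #1 successes, subject to the unseen part of the exclusion list. It deserves correction because it concerns the counting rule of a primary endpoint and is cheap to close.

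Its size is unknown. Under the assumed shares, a 1-point between-phase difference is negligible, 2 points gives about 6% rejection under the null and 3 points about 10%. Equal shares of 2% or 5% cut power from 77% to 71% or 63%, but only if the planning rates are new-diagnosis rates.

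A reader might infer that the trial did enroll such patients, that the bias favors Phase II, or that the false-positive rate is near 20%. The documents support none of these. They give no share and no direction, and the 19–23% figures need a third to a half of Phase II diagnoses to precede consent. Confidence is medium.

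**What to change.** - **Section 11.1 part B, Objective #1:** restrict the primary numerator and denominator in both phases to subjects with no SND diagnosis before consent. Keep diagnoses made after consent on the same day. Report by phase the number already diagnosed at consent, and give the all-enrolled result as a sensitivity analysis.
- **Objective #2 (11.1) and the secondary objective (11.2):** count only referrals and implants made after consent. Leave out subjects already referred (Objective #2) or already implanted (secondary objective) at consent. Start the Poisson offset in both sections at the later of consent and SND diagnosis.
- **Section 5.3:** leave enrollment open. These objectives use only diagnosed subjects, about 20 and 40 per 200 at the planned rates. With an assumed 5% already diagnosed in both phases, there would be up to 200 × 0.145 = 29 and 200 × 0.24 = 48, less those already referred or implanted, against 19 and 38 if all were lost.
- **CRF:** add one item for the order of consent and diagnosis.
- **Section 4.4:** state that selective invitation of patients suspected of SND but not yet diagnosed is not removed and remains a limitation.

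**Cost.** A few sentences and one CRF item. The Objective #1 set is slightly smaller: power is 75% or 72% if 5% or 10% are removed from both phases. The loss is greater if the removed diagnoses are mostly Phase II intervention effects: power is 64% if 10% of Phase II diagnoses and none in Phase I are removed. The rule also relies on unblinded sites to record the order correctly.

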5.4. Diagnostic Assessment Visit(s)

A diagnostic assessment is any post enrollment visit to the study center for continued diagnostic assessment or management. During these visits information about utilization of diagnostic tests, results and cardiovascular medication use will be collected. Information about the final diagnosis and treatment decision will also be collected during the diagnostic assessment visit. The diagnostic assessment visit data will be complete:

- When the subject meets study exit criteria
- 6 months after the last Phase I enrollment for Phase I subjects
- 6 months after the last Phase II enrollment for Phase II subjects
- Patient education tools have been reviewed with the patient by the investigator (Phase II only)

The study protocol does not dictate when the Diagnostic Assessment(s) is/are to occur.

5.5. Implant Visit

The implant visit is when the IPG is implanted in the study subject and will only occur for those subjects meeting the ACC/AHA/HRS and ESC pacing indications for sinus node dysfunction.

The implant will be performed according to the hospital's standard implant practice. Brady MX does not have device programming requirements. Information about the device and lead configuration, as well as serial number will only be collected for Medtronic and Vitatron devices.

5.6. Study Exit

Subjects may be exited from the study for any of the following situations, including but not limited to:

- Subject does not meet an indication for pacing therapy
- Subject meets an indication for pacing but not a SND indication for pacing therapy

- Subject has met a SND indication for pacing therapy but will not be receiving pacing therapy
- Subject diagnosis meets an SND indication for IPG Therapy and a non-Medtronic/Vitatron device was implanted.
- Completion of study follow-up with no diagnosis made
- Study Closure
- Subject lost to follow-up, patient doesn't come back after baseline for diagnosis test decision
- Subject death
- Subject did not meet inclusion/exclusion criteria
- Subject chooses to withdraw (e.g., consent withdrawal, relocation to another geographic location)
- Investigator deems withdrawal necessary (e.g., medically justified, failure of subject to maintain adequate study compliance)

